8.3 Definitions

In the following table, the required definitions and calculation for derivation during the analysis are summarized.

Document Title:	Statistical Analysis Plan		
Version Number:	Final 1.0	Date:	18Oct2024
Protocol Number:	SARO.17.009	Sponsor Name:	Zydus Therapeutics INC

Term	Definition / Way of Calculation
Baseline	Baseline is defined as the last non-missing observation (including scheduled and unscheduled assessments within the pre-treatment period) prior to the first dose administration of study drug.
Change from Baseline	Post Baseline Value - Baseline value.
Percentage Change From Baseline	$\frac{(\text{Post Baseline} - \text{Baseline})}{\text{Baseline}} \times 100$
Treatment Start Date/time	Date/time of first dose administration in the study.
Treatment End Date/time	Date/time of last dose administration in the study.
Treatment Emergent Adverse Event (TEAE)	Treatment-emergent AEs are defined as any AE that started after the first dose of study drug or started before the first dose but increased in severity or frequency after administration of the initial dose of study drug.
Duration of Treatment (Days)	Treatment End Date – Treatment Start Date + 1.
Duration of Study (Days)	Last Visit Date – Informed Consent Date + 1.

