4.2 INCLUSION CRITERIA

1. Females, 18 to 45 years of age.
2. Previously confirmed diagnosis of PCOS by Rotterdam criteria¹⁷ (at least 2 of 3):
 - 1) oligo-and/or anovulation;
 - 2) hyperandrogenism (clinical and/or biochemical);
 - 3) polycystic ovary morphology on ultrasonography (either 12 or more follicles measuring 2–9 mm in diameter or an increased ovarian volume >10 cm³).
3. Evidence of NAFLD within 6 months prior to the Screening Visit (Visit 1). The diagnosis of NAFLD is made according to the American Association for the Study of Liver Diseases criteria.¹⁸
 - a) hepatic steatosis by imaging or histology,
 - b) no significant alcohol consumption,
 - c) no competing etiologies for hepatic steatosis, and
 - d) no co-existing causes for chronic liver disease.
4. Alanine transaminase ≥ 38 U/L at Visit 1. Visit 2 ALT must not increase $>30\%$ from Visit 1.
5. Hepatic fat fraction $\geq 10\%$ by MRI-PDFF.
6. Willingness to participate in the study.
7. Ability to understand and give informed consent for participation.
8. A normal pelvic examination within past 6 months before randomization.
9. A normal breast examination at screening (If Mammogram has been done in the preceding 12 months it will be documented. If patient is not up to date with standard breast cancer screening guidelines and is willing to receive screening, mammogram

 Zydus Discovery DMCC	CLINICAL TRIAL PROTOCOL Saroglitazar Magnesium – Phase 2A SARO.17.009	Confidential Page 40 of 82
--	---	-------------------------------

will be offered prior to enrollment as part of standard care).

10. A normal Papanicolaou (PAP) test within past 6 months before randomization (If PAP test has not been performed within 6 months of the screening visit, it must be performed during screening).
11. Woman who agrees to use the following contraceptive methods:
 - a. Combination hormonal contraceptives (including pills, patches and vaginal rings). For the following conditions, the usage of the combination hormonal contraceptives should be based upon a discussion with the subject and the investigators' clinical judgment.
 - i. Women greater than 35 years of age who also smoke fewer than 15 cigarettes per day
 - ii. Adequately controlled hypertension
 - iii. Properly taken blood pressure above a systolic 140-159 mm Hg or diastolic 90-99 mm Hg
 - iv. Known hyperlipidemia
 - v. Diabetes associated with vascular disease, including neuropathy, retinopathy and nephropathy.

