Visit 2 (Day -14 to -7): Liver function tests (AST, ALT, ALP, GGT, total protein, albumin, total bilirubin (with conjugated bilirubin) will be re-measured approximately 2 weeks from Day - 28 to determine eligibility.

Alanine transaminase ≥ 38 U/L at Visit 1. Visit 2 ALT must not increase $>30\%$ from Visit 1.

Randomization and Treatment Phase

Visit 3 to Visit 8: The randomization and treatment phase will include 6 outpatient visits (Visit 3 to Visit 8) over a period of 24 weeks including the randomization visit. All the eligible subjects will be randomly assigned into either of the two treatments arms: Saroglitazar Magnesium 4 mg Tablets and matching placebo tablets in a 1:1 ratio. Efficacy assessments will be conducted at 12 (hormonal profile, lipid and lipoprotein profiles, ovarian function and liver enzymes/LFTs) and 24 weeks visits (liver fat content by MRI-PDFF, hormonal profile, lipid and lipoprotein profiles, MRI-derived total liver fat index and total liver volume, homeostasis model assessment [insulin resistance (HOMA-IR)], liver stiffness by transient elastography/FibroScan®, controlled attenuation parameter, ovarian function and liver enzymes/LFTs). In addition, subjects will be monitored during the study and at every visit for development of any adverse events including drug induced liver injury. In addition to physical examination, laboratory data and ECGs done during the study period will be monitored to detect any treatment emergent adverse events.

Visit 3 (Week 1, Day 1): Patients will be randomly assigned to receive Saroglitazar Magnesium 4 mg Tablets or placebo orally once-daily, starting on Day 1 of a 24-week outpatient treatment period.

Visits 4, 5, 6, 7 and 8: Patients will visit the study site at Week 2 (Visit 4), Week 8 (Visit 5) Week 12 (Visit 6), Week 16 (Visit 7) and Week 24 (Visit 8) for clinical assessment, dispensation and reconciliation of study drug, measurements of efficacy endpoints and assessment of AEs.

Detailed efficacy and safety assessments are provided in Table 1 (Time and Events Schedule).

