This document describes the statistical methods and procedures to be implemented for the analysis of data from SARO.17.009 study. The plan has been developed after review of the clinical study protocol, Version No. 5.0, Dated 06th February 2020 and Case Report Form (CRF) final Version No. 1.7, Dated 28th April 2020. This Statistical Analysis Plan is written with consideration of the recommendations outlined in the International Conference on Harmonisation (ICH) E9 guideline entitled “Guidance for Industry: Statistical Principles for Clinical Trials”, ICH E9 (R1) guideline entitled “Addendum on estimand and sensitivity analysis in clinical trials” and the ICH E3 guideline entitled, “Guidance for Industry: Structure and Content of Clinical Study Reports (CSR). This Statistical Analysis Plan (SAP) was developed prior to database lock.

Any changes from the planned analysis as described in the protocol are detailed here, and any differences described here supersede the analysis as presented in the protocol. Any deviations from the planned analyses described in this SAP will be documented in the clinical study report, together with the reason for such changes.

Prior to start of any statistical analyses, the database must be authorized and all decisions regarding assignment of participants to study populations must be completed. In addition, protocol deviations must be identified prior to the start of statistical analyses.

Document Title:	Statistical Analysis Plan		
Version Number:	Final 1.0	Date:	18Oct2024
Protocol Number:	SARO.17.009	Sponsor Name:	Zydus Therapeutics INC

6 Study Objectives and endpoints

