Note: Efficacy assessments and laboratory assessment (liver fat content by MRI-PDFF [MRI-PDFF will be performed during screening phase, screening phase results will be used as the baseline assessment], controlled attenuation parameter, hormonal profile, fasting plasma glucose, lipid and lipoprotein profiles, MRI-derived total liver fat index and total liver volume [MRI derived total liver fat index and total liver volume assessment will be performed during screening phase, screening phase results will be used as the baseline assessment], plasma insulin levels, homeostasis model assessment -insulin resistance [HOMA-IR], liver stiffness by transient elastography/FibroScan®, ovarian function, liver enzymes/LFTs, hematology, coagulation test (PT/INR), renal function test, CK, hs-CRP, BNP , NT-proBNP, cardiac troponin, CK-MB, lipase and amylase, TNFa, uric acid, TSH, T3 and T4, serology, HIV type 1 and type 2, HAV, antiHBsAg, HCV, serum pregnancy test, urine microscopy and urine chemistry) which will be done at Visit 1 will be considered for baseline visit. PAP test, endometrial biopsy and mammography will be performed as per Time and Events Schedule (refer **Appendix 1**).

Document Title:	Statistical Analysis Plan		
Version Number:	Final 1.0	Date:	18Oct2024
Protocol Number:	SARO.17.009	Sponsor Name:	Zydus Therapeutics INC

7 Study Design

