9.8.2 Laboratory Parameters

Clinical laboratory assessments for renal function test, creatine kinase, urinalysis, BNP, NT-pro BNP, cardiac troponin, CK-MB, Lipase and Amylase will be performed at the Screening, Baseline, Week 2, Week 8, Week 12, Week 16 and Week 24 visits. Laboratory assessments for hs-CRP, TSH, T3, T4 and TNF α will be performed at the Screening and Week 24 visits. All other laboratory assessments will be performed at

Document Title:	Statistical Analysis Plan		
Version Number:	Final 1.0	Date:	18Oct2024
Protocol Number:	SARO.17.009	Sponsor Name:	Zydus Therapeutics INC

Screening, Week 12 and Week 24 visits. Laboratory values will be presented using the International System of Units (SI units).

Observed and changes from baseline values will be summarized descriptively (n, mean, median, standard deviation, minimum, and maximum values) at each assessment. A summary table of the categorical grade shift changes using the normal ranges from baseline to last study visit will be provided based on safety population.

Additionally, A summary of frequency count and percentages for abnormal liver enzyme parameters at each visit as well as worst value across all visits up to EOT will be provided by treatment group for the following categories.

- ALT $\geq 3 \times$ ULN, $\geq 5 \times$ ULN and $\geq 10 \times$ ULN
- AST $\geq 3 \times$ ULN, $\geq 5 \times$ ULN and $\geq 10 \times$ ULN
- Total Bilirubin $> 2 \times$ ULN
- ALT $\geq 3 \times$ ULN and Total Bilirubin $\geq 2 \times$ ULN
- ALT $\geq 3 \times$ ULN and Total Bilirubin $\geq 1.5 \times$ ULN
- AST $\geq 3 \times$ ULN and Total Bilirubin $\geq 2 \times$ ULN
- AST $\geq 3 \times$ ULN and Total Bilirubin $\geq 1.5 \times$ ULN
- ALP $> 1.5 \times$ ULN

A summary of abnormal liver enzyme parameters for patients with elevated ALT or AST at baseline (elevated at baseline is defined as, baseline ALT or AST $\geq 1.5 \times$ ULN) at each visit as well as worst value across all visits up to EOT will be provided by treatment group using frequency count and percentage for the following categories.

- ALT $> 5 \times$ baseline value at post-baseline visits
- ALT $> 3 \times$ baseline value at post-baseline visits
- ALT $> 2 \times$ baseline value at post-baseline visits with either a concomitant Total Bilirubin increase $> 2 \times$ ULN or INR increase by > 0.2
- AST $> 5 \times$ baseline value at post-baseline visits
- AST $> 3 \times$ baseline value at post-baseline visits

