9.9 Subgroup Analyses

Primary endpoints i.e., Change in hepatic fat content, and following secondary endpoints will be analyzed across subgroups using the same analysis as specified for the primary and secondary endpoints., PP and mITT analysis population will be used for subgroup analysis.

1. Liver Enzymes/LFTs (ALT, AST, ALP, GGT, serum protein, albumin, and total bilirubin)

Document Title:	Statistical Analysis Plan		
Version Number:	Final 1.0	Date:	18Oct2024
Protocol Number:	SARO.17.009	Sponsor Name:	Zydus Therapeutics INC

2. Liver stiffness measurement obtained via transient elastography/ FibroScan®
3. MRI-derived total liver fat index and total liver volume
4. Serum lipid profile and lipoproteins (TG, TC, HDL, LDL, sdLDL, VLDL, ApoA and ApoB)

The subgroups are defined as follows:

a) ALT Scores

- ALT values at baseline ≥ 38
- ALT values at baseline < 38

b) Geographical region (Country):

- Mexico
- USA

Document Title:	Statistical Analysis Plan		
Version Number:	Final 1.0	Date:	18Oct2024
Protocol Number:	SARO.17.009	Sponsor Name:	Zydus Therapeutics INC

10 Deviation from the Study Protocol

The planned analysis will be performed according to the study protocol, its amendments and this statistical analysis plan. Contradictions between the study protocol or its amendments and this statistical analysis plan, the analysis will be performed according to this analysis plan. Any deviation from the planned analysis according to the study protocol has to be reported.

The differences between study protocol and statistical analysis plan are summarized in the following table:

Change	Study protocol	Statistical analysis plan
The terminology Patient(s) and Subject(s) has been replaced with Participant(s) throughout the document.	Patient(s) and Subject(s) has been used.	Used Participant(s) instead.
Missing values imputation	LOCF has been defined for primary and secondary variables imputation.	Only primary variable will be imputed with missing values by using multiple imputation method and secondary variables will be analysed as observed.
Subgroup analysis	No subgroup analysis strategy has been defined.	Primary and defined secondary efficacy analysis endpoints will be analyzed across subgroups as defined in section 9.9 using the same analysis as specified for the primary and secondary endpoints.
Estimand	No estimand framework has been defined	Estimand framework for primary efficacy endpoint has been defined in the SAP.

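### SAP 6.3 and 8.3 set different liver-test baselines; under 8.3 the ALT strata only partly match the Visit 1 criterion they examine, and the difference between strata is not itself estimated

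*SAP*

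**What the plan says.** **Baseline.** The note closing SAP 6.3 lists liver enzymes among the assessments "which will be done at Visit 1 will be considered for baseline visit". The derivation table in SAP 8.3 says: "Baseline is defined as the last non-missing observation (including scheduled and unscheduled assessments within the pre-treatment period") before the first dose. It makes no exception for liver tests. Protocol 4.5 names Visit 2 as the liver-test baseline for safety.

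**When ALT is measured before dosing.** At Visit 2 (Day -14 to -7) the liver tests "will be re-measured approximately 2 weeks from Day" -28 (protocol 7.2). SAP 9.8.2 lists the tests drawn at the Baseline visit, and liver tests are not among them: "All other laboratory assessments will be performed at" "Screening, Week 12 and Week 24 visits. Laboratory values will be presented".

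**Entry criterion.** Protocol 4.2, criterion 4, requires ALT of at least 38 U/L at Visit 1. It then says "Visit 2 ALT must not increase" by more than 30% from Visit 1. That is a ceiling; Visit 2 has no lower limit.

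**Strata.** SAP 9.7.1.2 notes that women recruited before the amendment may not meet the ALT criterion. It says a stratum analysis, or a covariate adjustment, will assess whether the change influenced the treatment effect. SAP 9.7.1.6 and 9.9 split on baseline ALT at 38 without naming a visit. They apply the primary ANCOVA within each stratum.

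**Precedence.** SAP 5 says "any differences described here supersede the analysis as presented in the protocol". SAP 10 says that where protocol and SAP contradict each other "the analysis will be performed according to this analysis plan". Its table of differences has no entry on baseline.

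**The concern.** The two SAP rules pick different ALT values for anyone with a Visit 2 result, and both precedence clauses rank the SAP over the protocol only. They cannot settle a conflict inside the SAP.

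The strata exist to examine a criterion applied at Visit 1. If they are built on a later value, the <38 group mixes women who would not meet the present Visit 1 limb with women who did.

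Whether a criterion change influenced the treatment effect is also a question about the difference between two stratum effects. Separate fits give two effects and no estimate of that difference. Adjusting for ALT as a covariate does not estimate it either.

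What is at stake is how well one supportive check answers its own question. The same open baseline also feeds the change scores of the seven liver tests in SAP 9.7.2.1, although randomisation protects the between-arm comparison under either rule.

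**Working it through.** The plan prints no figure on this point, so the check is a comparison of texts followed by a sizing under stated assumptions.

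**1. Which ALT is baseline?**

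| Rule | Value selected | Stratum if Visit 1 = 40 and Visit 2 = 36 |
|---|---|---|
| SAP 6.3 | Visit 1 | ≥38 |
| SAP 8.3, no later pre-dose draw | Visit 2 | <38 |

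The woman is eligible: 40 ≥ 38, and (36 − 40)/40 = −10%, which does not breach the 30% ceiling.

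**2. How many women cross?** All inputs here are assumptions, because the documents give no ALT distribution, stratum sizes or amendment split. ALT is lognormal with median 45 to 70 U/L, between-person log-SD 0.3 to 0.5 and within-person CV 10% to 30%. Twenty-seven combinations were simulated with 2 million draws each. Women under the current criterion are conditioned on Visit 1 ALT 38 to 250, Visit 2 ≤ 250 and Visit 2 ≤ 1.3 × Visit 1. Earlier women have no lower limit and no 30% rule. Of women eligible under the current criterion, 1% to 27% have Visit 2 ALT below 38.

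Central case: median 55, log-SD 0.4, CV 20%, 60 women, 30 under each regime.

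- Current criterion, Visit 2 <38: 30 × 0.104 = 3.12 women, all with Visit 1 ≥38.
- Earlier recruits, Visit 2 <38: 30 × 0.2037 = 6.11, of whom 30 × 0.0711 = 2.13 had Visit 1 ≥38.
- Share of the <38 stratum with Visit 1 ≥38: (3.12 + 2.13)/(3.12 + 6.11) = 5.25/9.23 = 57%.

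That assumes earlier recruits also had a Visit 2 test. If they had Visit 1 only, 30 × 0.2039 = 6.12 of them are <38 and none crosses, so the share is 3.12/(3.12 + 6.12) = 34%.

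Across all combinations at the half-and-half split, the share is 25% to 86% with a Visit 2 test for earlier recruits and 16% to 50% without one. In the 86% combination the whole <38 stratum holds about 4 women.

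**3. Precision of the between-stratum difference.** Completers: 60 × 0.8 = 48, or 24 per arm. The SD of 6 points is an assumption. Solving the noncentral t for 37 per arm, a 4-point difference, 80% power and two-sided 5% gives 6.06; the printed SD is 0.6. With a and b completers per arm in the two strata:

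- stratum half-width = t(0.975, 2n − 3) × 6 × √(2/n);
- one-model interaction half-width = t(0.975, 43) × 6 × √(2/a + 2/b), where 43 = 48 − 5 parameters;
- subtraction of separate fits: same standard error, Satterthwaite df 42.0, 15.5 and 3.9.

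| a/b per arm | Stratum half-widths | By subtraction | One model |
|---|---|---|---|
| 12/12 | 5.1 / 5.1 | 7.0 | 7.0 |
| 18/6 | 4.1 / 7.8 | 8.5 | 8.1 |
| 21/3 | 3.7 / 15.6 | 14.7 | 10.6 |

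Power to detect a 4-point interaction is 0.20, 0.17 and 0.12 respectively.

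**The case against.** The case for leaving this alone has substance.

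- *The conflict is one unreconciled sentence.* The 6.3 note repeats almost unchanged a note in protocol 3.3 and sits under safety objectives. Section 8.3 is the derivation table, which a programmer would follow. That stands as a reason to expect 8.3 to prevail, but following 8.3 is what produces the mismatch in the strata.
- *The sizing is soft.* A reader might infer that the <38 stratum is mostly women who met the criterion. The documents do not support that. They give no ALT data, and they do not show that women recruited before the amendment had a Visit 2 test. The highest percentages also come from very small strata.
- *Visit 2 may not be the last draw.* The schedule table is not shown, and SAP 9.8.2 also tabulates liver enzymes at each visit, which fits poorly with draws only at Screening, Week 12 and Week 24. If liver tests are also drawn at Visit 3, the simulated figures do not apply; the mismatch with Visit 1 remains.
- *The between-stratum difference can be derived.* A reader might infer that the plan leaves its question unanswerable. It does not: both stratum effects and their intervals are reported, and subtraction is nearly as precise as one model unless one stratum is very small. The one-model gain there also relies on a common residual variance.
- *Visit 1 strata are imperfect too.* They ignore the 30% limb of criterion 4 and do not identify enrolment before or after the amendment.

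These points limit the size of the issue. They do not remove the conflict or supply the missing estimate.

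**Conclusion.** The point holds as a minor one. SAP 6.3 and 8.3 disagree on the liver-test baseline and the SAP does not say which governs. Under 8.3 the strata only partly match the Visit 1 criterion, and the comparison that 9.7.1.2 asks for is left to the reader.

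The number of women affected cannot be known from the documents. The central figure of about 3 to 5 of 60 rests on the assumed ALT distribution, an assumed half-and-half split, Visit 2 as the last pre-dose test, and on whether earlier recruits had that test.

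A reader might infer that the trial's main conclusion is at risk. It is not: the primary ANCOVA uses baseline hepatic fat, not ALT, and the harm is confined to a supportive check that is imprecise however it is done.

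**What to change.** 1. In SAP 9.7.1.6 and 9.9, define the ALT strata from Visit 1 ALT. No woman with Visit 1 ALT of 38 or more can then sit in the <38 stratum.
2. Add one ANCOVA with treatment, baseline value, stratum and treatment-by-stratum. Report the interaction estimate and its 95% CI descriptively beside the stratum estimates.
3. In SAP 8.3, name one efficacy baseline for liver tests so that 6.3 and 8.3 agree.
4. State which baseline the multiples-of-baseline tables in SAP 9.8.2 use and reconcile it with protocol 4.5. Which value suits safety is for the sponsor to decide.

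The cost is SAP wording and one added model; Visit 1 ALT is already collected. Two cautions belong in the text. The interaction interval will be wide, about ±7 to 11 points if the SD is 6 and 48 complete, so a non-significant result must not be read as no influence. And Visit 1 strata capture neither the 30% limb nor the timing of enrolment relative to the amendment.

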8.4 Handling of Dropouts and Missing data

Clarifications, wherever possible, will be obtained from the respective Investigator or data management team for any missing data or for any illegible entry, unused or unauthenticated data and this will be recorded in the data handling report (If required) before the final database lock.

Dropouts and missing values, considering missing values as missing at random (MAR) will be imputed by using multiple imputation method for primary efficacy variable, for mITT population only, and will be considered as supportive to the analysis.

Dropouts and missing values will not be imputed for safety and secondary endpoints.

Imputed data should be flagged and properly footnoted as “imputed”. Title should indicate that imputed data is used for summary.

Adverse events with unknown end date/time will be counted as an ongoing AEs, if ongoing is ticked on the CRF. Medications with unknown end date/time will be considered as concomitant. Adverse events and medications with partially missing start or end dates will be considered ongoing and concomitant respectively unless the non-missing portion of the dates definitively proves otherwise.

Document Title:	Statistical Analysis Plan		
Version Number:	Final 1.0	Date:	18Oct2024
Protocol Number:	SARO.17.009	Sponsor Name:	Zydus Therapeutics INC

Partial dates for Adverse events and medications will be imputed as follows for derivation of treatment emergent and Prior/Concomitant flags respectively:

- Missing day in start date of a time period is imputed by the first day of the month.
- Missing day in end date of a time period is imputed by the last day of the month.
- Missing month in start date of a time period is imputed by January of the year.
- Missing month in end date of a time period is imputed by December of the year.
- Missing year is not imputed.
- After above imputation if start or end date is after Participant's end of study date then start or end date is set to Participant's end of study date.

If required, time will be imputed in the following way:

Times should be printed in the format "HH:MM". "HH" represents the 2-digit hour portion of the time. "MM" represents the 2-digit minute portion of the time. Both hour and minute portions of time are zero padded integer values. Missing time portions should be represented on Participant listings as dashes ("10:--" and "--:--").

Missing or partial dates for medical history findings will not be completed by imputation, for example, if only a month and year are available as --FEB2019, the day will not be imputed. If "Stop Date" information is not available, it will be assumed that the finding is "Ongoing" at the time of enrollment in the study.

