8.4.3 Safety Analysis

All safety analysis will be carried out on the safety population. The frequency tabulations of abnormal clinical laboratory values for the parameter will be presented for each treatment group by visit. Summary statistics for clinical laboratory parameters, ECGs, physical examination and vital signs will be presented for each treatment by visit.

All AEs observed during the study period will be listed. Incidence of all AEs reported during the study will be summarized using the MedDRA (version 19 or higher) by treatment group, frequency, severity, seriousness, relationship to study drug and expectedness per System Organ Class and Preferred Term.

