9.4 PROCEDURES

9.4.1 Adverse Events

Adverse event reporting will begin after the informed consent has been signed and will continue until end of the study (i.e., the safety telephone call). The Common Terminology Criteria for Adverse Event (Version 4.03 or higher) system will be used for reporting and grading AEs.

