9.8 Safety Analysis

9.8.1 Adverse Events

The applicable definition of an Adverse Event (AE) is any unfavorable or unintended sign, symptom or disease temporally associated with the use of study drug whether or not considered related to study drug, as per the study protocol. Treatment-emergent AEs are defined as any AE that started after the first dose of study drug or started before the first dose but increased in severity or frequency after administration of the initial dose of study drug. The period for treatment-emergent AE analysis starts from the first exposure to the study drug until the participant exits the study.

All the AEs, serious adverse events (SAEs), treatment emergent adverse event (TEAEs) and expected adverse event reported throughout the study, shall be coded and classified according to the standards of latest version of MedDRA (Medical Dictionary for Regulatory Activities) and grouped by preferred term (PT) and system organ class (SOC).

All adverse events for each participant, including the same event on several occasions should be listed for safety population giving both preferred term and original term used by the investigator.

The summary of frequency counts of the number of adverse events (E), and the number of participants with adverse events (n), and the percentages (%) for the number of participants with adverse events will be presented for treatment groups and for overall. For the summaries which count the number of participants, if a participant has more than one TEAE the participant will be counted only once in accordance with SOC and PT. When AEs occur more than once for a participant, the maximal severity (Maximum severity between severity and CTCAE Grade will be considered) and the strongest relationship to the treatment group will be counted. Safety analysis population will be used for adverse events summary tables.

In addition to an overall presentation of all TEAEs, reports will be generated for special classes of TEAEs as follows:

- Overall Summary of AEs
- TEAEs by SOC and PT
- Serious TEAEs by SOC and PT
- TEAEs leading to death by SOC and PT
- TEAEs leading to permanent discontinuation by SOC and PT
- TEAEs by SOC, PT and by Strongest Relationship to Study Drug
- TEAEs by SOC, PT and by Maximum Severity

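### SAP 8.4 dates partial AE start dates to the 1st of the month or to January without comparing them with first dose, so some post-dose events are flagged as not treatment-emergent

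*SAP*

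**What the plan says.** SAP 8.4 states what its partial-date rules are for: "Partial dates for Adverse events and medications will be imputed as follows for derivation of treatment emergent and Prior/Concomitant flags respectively". They therefore determine analysis status and are not only for display.

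For start dates, "Missing day in start date of a time period is imputed by the first day of the month" and "Missing month in start date of a time period is imputed by January of the year". A missing year is left alone. The only check after imputation is an upper bound: a date later than the participant's end of study is pulled back to it. There is no lower check against first dose.

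SAP 8.3 defines a TEAE as "any AE that started after the first dose of study drug", or an earlier event that worsened in severity or frequency after that dose. SAP 9.8.1 adds "The period for treatment-emergent AE analysis starts from the first exposure to the study drug until the participant exits the study" and gives no partial-date rule of its own.

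Pre-dose events will exist, because "Adverse event reporting will begin after the informed consent has been signed" (Protocol 9.4.1). The flag therefore has real work to do.

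**The concern.** Moving an unknown start to the earliest possible date is cautious for medications, because it does not take them out of the concomitant group. For adverse events the same shift works the other way. It can move a new on-treatment event to before first dose, and the worsening limb of the definition does not rescue a new event.

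SAP 8.4 does keep partially dated AEs as ongoing and partially dated medications as concomitant "unless the non-missing portion of the dates definitively proves otherwise". Neither label says whether an AE began after first dose, so the TEAE flag has no equivalent protection.

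Six of the seven reports listed in SAP 9.8.1 are TEAE tables: all events, serious, fatal, leading to discontinuation, by relationship and by severity. Affected events would be missing from all that apply to them, and reported TEAE incidence would be too low. The loss falls mainly in the first weeks on drug.

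**Working it through.** The documents give no figure for this rule, so there is none to reproduce. The check applies SAP 8.4 and SAP 8.3 to calendar dates.

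**Worked example** (illustrative first dose 5 March 2020)

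| True onset | Recorded as | Imputed start | TEAE flag |
|---|---|---|---|
| 20 March 2020 | March 2020 | 1 March 2020 | No (wrong) |
| 2 April 2020 | April 2020 | 1 April 2020 | Yes |
| 15 August 2020 | 2020 | 1 January 2020 | No (wrong) |

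**Inputs.** Day 1 is first dose, treatment ends on Day 168 and follow-up ends on Day 210 (SAP 7.1). Screening lasts 28 days (SAP 7.2). Assumptions not in the documents: first doses fall evenly on the 365 dates of a non-leap year, and onset is uniform within each window.

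**Day missing.** With first dose on day *d* of a month of *L* days, the post-dose days that would be misdated number *L* − *d*. The count is 0 if *d* = 1, because the imputed date then equals the first-dose date and the status is ambiguous (12/365 = 3.3% of dates). The sum per month is (*L* − 1)(*L* − 2)/2:

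- seven 31-day months: 7 × 435 = 3,045
- four 30-day months: 4 × 406 = 1,624
- February: 351
- total 5,020, and 5,020/365 = **13.75 days** per participant

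The share of post-dose onset days misdated is then:

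- Days 2–168: 13.75/167 = **8.2%**
- Days 2–210: 13.75/209 = **6.6%**
- Days 2–14 (13 days, exposed days capped at 13): 3,497/(365 × 13) = **73.7%**
- Days 2–28 (27 days, capped at 27): 4,995/(365 × 27) = **50.7%**

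**Only the year known.** The share of post-dose days in the first-dose year, with 0 for a first dose on 1 January, is:

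- to Day 168: 46,760/(365 × 167) = **76.7%**
- to Day 210: 54,131/(365 × 209) = **71.0%**

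**Events lost.** These shares apply only to events whose date is already partial, so they must be multiplied by the proportion of TEAEs whose start day is still missing after query. That proportion is unknown; the range below is assumed.

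| Start day still missing | TEAEs lost, Days 2–168 (× 8.2%) | TEAEs lost, Days 2–14 (× 73.7%) |
|---|---|---|
| 2% | 0.16% | 1.5% |
| 5% | 0.41% | 3.7% |
| 10% | 0.82% | 7.4% |

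**After the fix.** Wrongly excluded post-dose events fall to 0% in every window, for a missing day and for a missing month. The price is over-flagging of screening events. Of the 28 days before first dose, 5,348/(365 × 28) = 52.3% share its month and 96.0% share its year, before end dates are used.

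**The case against.** The strongest objection is size. With recruitment closed at 60 participants (SAP 8.5), a loss of 0.2% to 0.8% would be less than one event in an illustrative 100 TEAEs, and no document shows that any AE date will remain partial. SAP 8.4 and Protocol 8.1.5 send missing data back to sites, and Protocol 9.2.4 ties AE onset to source documents. Visit 4 is on Day 14, so recall should be best in the very window where the calendar share is highest; the 1.5% to 7.4% range assumes the same missing rate throughout. Year-only dates are less likely still. Serious events are the least exposed, being reportable within 24 hours of the site becoming aware (Protocol 9.4.2.1). All of this stands as a limit on size. It does not change what the rule does to the dates it exists to handle, those that queries failed to complete.

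A second objection is that the sentence on ongoing and concomitant status could be read as an on-treatment default. The wording pairs ongoing with AEs and concomitant with medications. Ongoing describes whether an event has ended, while the start-date rules that follow are the ones expressly tied to the treatment-emergent flag. This objection fails.

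Third, the fix trades one error for another: it protects 13.75 post-dose days per participant and exposes 5,348/365 = 14.65 pre-dose days to over-flagging. At equal daily AE rates, and before end dates are used, the misclassified counts could be similar. That is fair. The case for the fix is the direction of the error, since over-counting is the cautious choice in safety tables, and end dates will remove some of the over-flagged events.

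It is also true that affected events stay visible. They remain in the by-participant listing, in the SAP's overall AE summary and in the Protocol 8.4.3 summary ("Incidence of all AEs reported during the study will be summarized"). The primary analysis is untouched.

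**Conclusion.** The concern holds. As written, SAP 8.4 gives the wrong TEAE status to new post-dose events whose start is known only to the month or year of first dose, apart from the ambiguous case of a first dose on the 1st (or on 1 January for year-only dates). The error runs only towards under-counting.

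The expected loss is small: about 0.2% to 0.8% of TEAEs to Day 168, and 1.5% to 7.4% of those starting in Days 2–14. These figures rest on three assumptions: even spread of first doses, uniform onset, and 2% to 10% of start days unresolved. The mechanism itself needs none of them. The rule is identical in both arms and does not by itself favour either. The change should be made, because the error is definite and the correction is cheap, but it does not threaten the trial's main conclusion.

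**What to change.** Add to SAP 8.4:

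> If the start day is missing and the known month and year equal those of first dose, or the start month is missing and the known year equals that of first dose, set the AE start date to the first-dose date and flag the event as a TEAE, unless its end date (known, or imputed by the end-date rule) shows that it ended before first dose.

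Keep the current rules for all other partial AE start dates, for end dates and for medications. The explicit flag is needed because the definition asks for onset after first dose, which a date equal to first dose does not clearly meet.

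The cost is one sentence and a few lines of derivation code before database lock. The downside is that some true screening events with partial dates will be counted as TEAEs, under the same rule in both arms.

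A separate gap can be closed in the same edit: the SAP gives no TEAE default when the start year is missing.
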